#### 16.3 Immunogenicity

Blood samples for anti-drug antibody (ADA) analysis will be collected per the Schedule of Assessments in the Clinical Trial Protocol and tested for presence of anti-avelumab ADA. All samples will be screened for the detection of ADA and those detected will be subsequently evaluated for a confirmatory signal. If the sample is confirmed positive for ADA, it will be reanalyzed to determine the titer. Independently for each assay, the ADA results will be derived based on the algorithm in Table 16.

Subjects will be characterized by immunogenicity status based on the criteria in Table 17.

Table 16: Algorithm for the Derivation of ADA Results

Sample Screen Result	Confirmatory	Titer	Derived ADA Result
Negative	NA	NA	Negative
NR	NA	NA	NR
Positive	Negative	NA	Negative
Positive	NR	NA	NR
Positive	Positive	Number	Number
Positive	Positive	NR	Positive-TNR

NR = no result, NA = not applicable, TNR = titer no result.

Negative, number, or positive-TNR are valid results, while number and positive-TNR are considered as positive.

Table 17: Subject Characterization Based on ADA Results

Category	Definition	Subject at Risk (Denominator for Incidence)
Never positive	No positive results at any time point	Number of subjects with at least one valid result at any time point
Ever positive	At least one positive result at any time point	Number of subjects with at least one valid result at any time point
Pre-existing	A positive ADA result prior to treatment with avelumab	Number of subjects with valid baseline result
Treatment boosted	A positive ADA result prior to treatment with avelumab and the titer $\geq$ 8 * baseline titer while on avelumab treatment	Number of subjects with valid baseline and at least one valid post-baseline result
Treatment emergent	Not positive prior to treatment with avelumab and with at least one positive post-baseline result	Number of subjects with at least one valid post- baseline result and without positive baseline results (including missing, NR)
Transient positive	If treatment emergent subjects have (a single positive evaluation, or duration between first and last positive result <16 weeks) and last assessment not positive.	Number of subjects with at least one valid post- baseline result and without positive baseline results (including missing, NR)
Persistent positive	If treatment emergent subjects have duration between first and last positive result ≥16 weeks or a positive evaluation at the last assessment	Number of subjects with at least one valid post- baseline result and without positive baseline results (including missing, NR)

NR: Not reported;

The frequency and percentage of subjects in each category will be summarized by cohort dose level and overall. A listing will be prepared by dose level for subject IDs ever positive.

ADA results for ever positive subjects will be listed by cohort dose level:

- Overview on ADA status: Subject ID, age, gender, ADA Status, Study Day of Start of ADA response, Duration of ADA immunogenicity response (weeks)
- Listing of ADA and Ctrough concentrations: Subject ID, Visit and Visit Date, ADA result, Date
  of last prior avelumab infusion, Days since last avelumab infusion, Date of last available
  predose drug concentration at or before ADA assessment and corresponding drug concentration
- Listing of all PK concentrations, Subject ID, Visit name and Visit Date, timepoint, observed avelumab serum concentration, Actual date/time; Hours since last avelumab infusion.
- Listing of immunogenicity data and adverse events (AEs): Subject ID, age, gender, study
  treatment start and stop date, all dates with positive ADA result, AE start date, stop date,
  preferred term, CTCAE toxicity grade, seriousness, and applicable flags for immune-related
  adverse event (irAE), infusion related reaction (IRR), serious adverse event (SAE), or reason
  for permanent treatment discontinuation.

# 18 Appendices

# Appendix I - Description of the Case Definition for Assessment of irAEs and IRRs

# Immune-Related Adverse Events

Immune-related adverse events (irAEs) will be identified programmatically. AEs which satisfy all of the following criteria will be flagged as immune-related:

- 1) The AE preferred term matches a preferred term on the list of pre-selected MedDRA terms.
- The AE onset occurs after the first study drug administration and no more than 90 days after last dose.
- 3) On the AE eCRF page, the question "Is this an adverse event of special interest?" has the response "imAEs / autoimmune disorders" selected.

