AE/SAEs Observed in Association with Disease Progression

Progression of the disease/disorder being studied assessed by measurement of lesions on radiographs or other methods as well as associated clinical signs or symptoms (including laboratory abnormalities) should not be reported as an (S)AE, unless the participant's general condition is more severe than expected for the participant's condition and/or unless the outcome is fatal within the adverse event reporting period, as defined in Section 8.3.2 (Method of Detecting Adverse Events and Serious Adverse Events)

Adverse Events of Special Interest

Avelumab

Immune-related adverse reactions (immune-related pneumonitis, immune-related colitis, immune-related hepatitis, immune-related endocrinopathies [thyroid disorders, adrenal insufficiency, new onset type I diabetes mellitus, pituitary disorders]), immune-related nephritis and renal dysfunction and other immune-related AEs (myositis, myocarditis, Guillain-Barré syndrome, uveitis, pancreatitis, and myasthenia gravis/myasthenic syndrome) have been identified as Adverse Event of Special Interest (AESI) for avelumab.

Any AE that is suspected to be a potential immune-related adverse reaction will be considered an AESI. These AESI do not require expedited reporting unless they are serious. Should the AESI be serious, a SAE form should be filled and the reporting process for SAEs should be followed.

M3814

No AESI have been defined for M3814 to date.

Recording and Follow-Up of AE and/or SAE

It is important that each AE report include a description of the event, its duration (onset and resolution dates and also onset and resolution times, when it is important to assess the time of AE

onset relative to the recorded study intervention administration time), its severity, its causal relationship with the study intervention, any other potential causal factors, any treatment given or other action taken, including dose modification or discontinuation of the study intervention, and its outcome. In addition, serious cases should be identified, and the appropriate seriousness criteria documented. If an AE constitutes a DLT this is documented accordingly.

Specific guidance is in the eCRF Completion and Monitoring Conventions provided by the Sponsor.

Reporting Serious Adverse Events, Adverse Events of Special Interest and Dose-Limiting Toxicities

Serious Adverse Events

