### Definition of on-treatment period

The on-treatment period is defined as the time from the first dose of study treatment through the minimum of (last date of study intervention + 30 days, start day of new anti-cancer drug therapy - 1 day, death).

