#### 15.1.1 All Adverse Events

Adverse events will be summarized by worst severity per subject, using MedDRA PT as event category and SOC as summary category, in alphabetical order. If an AE is reported for a given subject more than once during treatment, the worst severity and the worst relationship to study treatment will be tabulated.

An overall summary table of AEs will be prepared and will tabulate the number and percentage of participants with AEs in the following categories:

- Any TEAE
- TEAEs related to study intervention (tabulated by relatedness to any study intervention, and individual study intervention components)
- Any serious TEAEs
- Serious TEAEs related to study intervention (tabulated by relatedness to any study intervention, and individual study intervention components)
- TEAEs with NCI-CTCAE severity Grade ≥ 3
- TEAEs related to study intervention with NCI-CTCAE severity Grade ≥ 3 (tabulated by relatedness to any study intervention, and individual study intervention components)
- TEAEs leading to death
- TEAEs related to study intervention leading to death (tabulated by relatedness to any study intervention, and individual study intervention components)
- Treatment-emergent AESIs overall and by category (see Section 15.2.4 for more details on summaries of AESIs)

In addition, tables summarizing the frequency of subjects with AEs, presented by SOC and PT, in the following categories will be prepared. Tables summarizing TEAEs related to study intervention will be created to summarize TEAEs related to any study intervention and will be repeated to summarize TEAEs related to specific study intervention components (M3814, avelumab, and, for Part B, RT).

- Any TEAE
- TEAEs by worst grade
- TEAEs related to study intervention
- Serious TEAEs
- Serious TEAEs related to study intervention
- TEAEs related to study intervention by worst grade
- TEAEs leading to death
- TEAEs related to study intervention leading to death

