# 15.2.4 Adverse Events of Special Interest

Analysis set: SAF

The frequency (number and percentage) of subjects with each of the following will be presented for treatment emergent irAEs, by dose level:

- irAEs leading to death, by SOC and PT
- irAEs, by SOC and PT
- irAEs leading to discontinuation, by SOC and PT
- irAEs, Grade ≥ 3, by SOC and PT
- irAEs by SOC and PT and worst grade
- Serious irAEs by SOC and PT

The listing of all irAEs will also be provided with the relevant information with a flag for irAEs with onset outside of the on-treatment period. A separate listing of irAEs with onset after the ontreatment period will also be provided.

The frequency (number and percentage) of subjects with each of the following will be presented for treatment emergent IRRs, by dose level:

- IRRs leading to death, by SOC and PT
- IRRs leading to discontinuation, by SOC and PT
- IRRs, by SOC and PT
- IRRs, Grade ≥ 3, by SOC and PT
- Serious IRRs, by SOC and PT

Timing of first onset of an IRR (infusion 1, infusion 2, infusion 3, infusion 4 or later) will be provided.

The listing of all IRRs will also be provided with the relevant information with a flag for IRRs with onset outside of the on-treatment period.

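### The irAE frequency tables stop 30 days after last dose, or earlier at new therapy, although the SAP's own irAE definition runs to 90 days and its term-list filter can drop investigator-suspected events

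*SAP*

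**What the plan says.** SAP Appendix I flags an AE as immune-related only if three conditions all hold. The first is "The AE preferred term matches a preferred term on the list of pre-selected MedDRA terms". The second is the time window, "The AE onset occurs after the first study drug administration and no more than 90 days after last dose". The third is that the investigator chose the immune/autoimmune category in the AESI question on the AE eCRF page.

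SAP 15.2.4 says that the irAE frequencies (overall, Grade 3 or higher, worst grade, serious, leading to discontinuation, leading to death) "will be presented for treatment emergent irAEs, by dose level". The overall AE table in SAP 15.1.1 likewise has a row for "Treatment-emergent AESIs overall and by category". Treatment-emergent is tied in SAP 15.1 to the on-treatment period, which SAP 9.1 ends at the minimum of "last date of study intervention + 30 days, start day of new anti-cancer drug therapy - 1 day, death".

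SAP 15.2.4 also plans a listing of all irAEs with a flag for onset outside that period, and adds: "A separate listing of irAEs with onset after the ontreatment period will also be provided".

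Protocol Appendix 4 is broader on what counts: "Any AE that is suspected to be a potential immune-related adverse reaction will be considered an AESI". Protocol 9.4.2 names irAEs as an item of their own in the secondary safety analysis. Its general AE summaries run from first dose to 30 days after the last study intervention, with no cut at new therapy.

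**The concern.** The case definition and the tables use different windows. An irAE that starts 31 to 90 days after last dose meets Appendix I, yet no frequency, grade, seriousness or discontinuation table counts it. The same is true of an event that starts within 30 days but after a new anti-cancer drug, so the loss falls most on participants who stop and move on quickly.

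The term-list condition is a separate loss. An event that the investigator suspects to be immune-related, but whose coded term is not on the list, fails Appendix I. It then leaves the irAE listings as well as the irAE tables, because both rest on the same definition.

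The irAEs are the class that the protocol names as of special interest for avelumab. The protocol also schedules a 90-day safety contact (Section 4.1.1.3) and collects AEs to the last long-term follow-up visit (Section 8.3.1), so the data for a 90-day rate are planned to exist.

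**Working it through.** The documents give no irAE rate to reproduce, so the check compares definitions and then looks at the size of one event.

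**1. The rules side by side**

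| Rule | Onset window | Other conditions |
|---|---|---|
| Protocol Appendix 4, avelumab AESI | none stated in the definition | suspected immune-related |
| Protocol 9.4.2, TEAE summaries | first dose to last intervention + 30 days | none |
| SAP Appendix I, irAE | after first dose to last dose + 90 days | term list and investigator flag |
| SAP 9.1 and 15.1, treatment-emergent | first dose to the earliest of last intervention + 30 days, day before new anti-cancer drug, death | onset or worsening in the period |
| SAP 15.2.4, irAE tables | must meet both SAP rules above | term list and investigator flag |

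**2. Window gap.** 90 − 30 = 60 days after last dose lie inside Appendix I but outside the tables, and more if a new drug starts before Day 30. 60/90 = 67% is a share of post-dose calendar days only.

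**3. Direction.** Call the investigator-suspected events S, the on-list events L, the Appendix I window W and the treatment-emergent events T. The tables count S∩L∩W∩T. This is contained in S∩L∩W (Appendix I), which is contained in S (Protocol Appendix 4). With the same denominator, the tabulated irAE rate can only be equal or lower. This takes the eCRF flag as the record of the investigator's suspicion.

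**4. Size of one participant.** The step is 100/n points. Protocol 6.6.2 and 6.6.4 expect 3 to 6 participants per dose level, and at most 30 (Part A), 24 (Part B) and 12 (Part FE).
- Dose level: 100/3 = 33.3; 100/6 = 16.7.
- Whole part: 100/30 = 3.3; 100/24 = 4.2; 100/12 = 8.3.

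**5. Illustration only.** None of these inputs is in the documents. Let p be the participant-level irAE risk (10% to 30%), f the share of these participants with onset only outside the on-treatment period (5% to 20%), and g the share failing the term-list/flag rule (0% to 20%), acting independently. The tabulated risk is p(1−f)(1−g).
- Mildest: 0.10 × 0.95 × 1 = 0.095, which is 5% lower in relative terms. The chance of missing at least one of 30 participants is 1 − (1 − 0.005)^30 = 0.14.
- Strongest: 0.30 × 0.80 × 0.80 = 0.192, which is 36% lower. The chance is 1 − (1 − 0.108)^30 = 0.97.

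The width of this range shows that the documents do not settle the size.

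**6. Declared changes.** SAP Section 7 says that the protocol's methods were adopted and lists only dropped PK parameters. The new-therapy cut is not there.

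**The case against.** A case definition wider than the main table window, with the remainder listed, is a coherent design. Four stronger readings are tempting, and the documents do not support them.

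- A reader might infer that the 90-day criterion has no effect. It does: it sets the outer limit of the flagged irAE listing and of the separate late-onset listing. Late irAEs that meet Appendix I are missing from rates, not from the report.
- A reader might infer that the 30-day limit breaks the protocol. It matches the protocol's own TEAE summaries, and no protocol text promises a 90-day irAE rate. The SAP's additions are the new-therapy cut and the term list; the investigator flag is close to the protocol's idea of suspicion.
- A reader might infer that two thirds of irAEs are lost. The 67% ignores the whole time on treatment, and no late-onset share is given.
- A reader might extend the point to all AESI rates. SAP 15.1 adds infusion-related reactions, which the AESI list in Protocol Appendix 4 does not contain, so the direction for total AESIs is open.

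The term list itself is not in the documents, so a loss through it is possible but not shown. An off-list treatment-emergent event would still appear in the general TEAE tables, and any off-list event in the listing of all AEs.

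There is also a sound reason to keep the shorter window as primary. The 90-day contact is by phone, while examination, chemistry and thyroid tests are scheduled at the 30-day visit and not at 90 days. Events after a new drug may be due to that drug.

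What stands is that no rate uses the SAP's own 90-day definition, that the new-therapy cut is undeclared, and that nothing reconciles the term list with the investigator's flag.

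**Conclusion.** The point holds for irAE rates, as a modest and inexpensive improvement in an exploratory trial with no hypothesis test. The irAE tables omit onsets after Day 30 and onsets after a new anti-cancer drug, and the term-list condition can remove events that Protocol Appendix 4 treats as AESIs. The direction is fixed (equal or lower). The size is not known, because it depends on the late-onset share and the term list, neither of which the documents give. A single omitted participant would move a dose-level rate by 16.7 points (n = 6) to 33.3 points (n = 3).

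One ambiguity adds to this. Appendix I does not say which intervention last dose refers to, and Protocol 7.1 lets M3814 continue after avelumab stops, so the 90 days could be counted from different dates.

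**What to change.** Keep the treatment-emergent irAE tables as primary. Then:

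1. In SAP 15.2.4, add a supplementary irAE frequency column by dose level over the Appendix I window (first dose to 90 days after last dose), with onsets after new anti-cancer therapy shown separately.
2. Add a row counting every event with the investigator's immune AESI flag, regardless of the term list.
3. In Appendix I, state which intervention last dose refers to.
4. Declare the new-therapy cut in SAP Section 7 as a change from Protocol 9.4.2. It applies to all treatment-emergent tables, not only those for irAEs.

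The cost is extra table shells and programming; no new data are needed. Reported irAE rates may look slightly less favourable. The added column rests on weaker ascertainment after Day 30 and, after new therapy, on events of mixed cause, and a footnote should say so.

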#### IRRs

Infusion related reactions are identified based on a list of MedDRA PTs and criteria on the timely relationship according to Table 18Table 18.

Table 18: Criteria for infusion related reactions

Infusion related reactions	Reactions - Considered when onset is on the day of study drug infusion (during or after the infusion) or the day after the study drug infusion (irrespective of resolution date):
	Infusion related reaction
	Drug hypersensitivity
	Anaphylactic reaction
	Hypersensitivity
	Type 1 hypersensitivity
	Signs and Symptoms - occurring on the day of study drug infusion (during or after the infusion) and resolved with end date within 2 days after onset
	Pyrexia
	Chills
	Flushing
	Hypotension
	Dyspnoea
	Wheezing
	Back pain
	Abdominal pain
	Urticaria

# Appendix II – NCI-CTC Gradable and Non-Gradable Safety Laboratory Test Parameters and Direction(s) of Abnormality

Table 19: NCI-CTC gradable parameters

Category	Parameter	Name in NCI-CTC	Direction(s) of abnormality	
Serum chemistry				
Electrolytes	Calcium	Hypocalcemia/Hypercalcemia	Low/High	
Electrolytes	Magnesium	Hypomagnesemia/Hypermagnesemia	Low/High	
Electrolytes	Potassium	Hypokalemia/Hyperkalemia	Low/High	
Electrolytes	Sodium	Hyponatremia/Hypernatremia	Low/High	
Enzymes/cardinal	Creatinine Phosphokinase	CPK increased	High	
Enzymes/cardinal	Lactate dehydrogenase	Blood lactate dehydrogenase increased	High	
Enzymes/liver	Alanine Aminotransferase	Alanine Aminotransferase increased *	High	
Enzymes/liver	Alkaline Phosphatase	Alkaline Phosphatase increased *	High	
Enzymes/liver	Aspartate Aminotransferase	Aspartate Aminotransferase increased *	High	
Enzymes/liver	Gamma-glutamyl transferase	GGT increased *	High	
Enzymes/liver	Total bilirubin	Blood bilirubin increased *	High	
Metabolism	Glucose	Hypoglycemia	Low	
Metabolism	Urate (uric acid)	Hyperuricemia	High	
Plasma proteins	Albumin	Hypoalbuminemia	Low	
Renal/kidney	Creatinine	Creatinine increased *	High	
Hematology				
Platelets	Platelets Count	Platelet count decreased	Low	
Red blood cells	Hemoglobin	Anemia/Hemoglobin increased	Low/High	
White blood cells/differential	White Blood Cell Count	White blood cell decreased/Leukocytosis	Low/High	
White blood cells/differential	Absolute Lymphocytes Count	Lymphocyte count decreased/increased	Low/High	
White blood cells/differential	Absolute Neutrophils Count	Neutrophil count decreased	Low	
White blood cells/differential	Eosinophils	Eosinophilia *	High	

\* indicates parameters for which the on-treatment grading depends upon the baseline grading.

Table 20: NCI-CTC non-gradable parameters

Category	Parameter (LBTEST)	Direction(s) of abnormality		
Serum chemistry				
Electrolytes	Phosphate	Low		
Metabolism	Glucose	High		
Plasma proteins	Total protein	Low		
Renal/kidney	Blood Urea Nitrogen	High		
Hematology				
Red blood cells	Hematocrit	High/Low		
Red blood cells	Mean Corpuscular Hemoglobin	High/Low		
Red blood cells	Mean Corpuscular Hemoglobin Concentration	High/Low		
Red blood cells	Mean Corpuscular Volume	High/Low		
Red blood cells	Red blood cells (Erythrocytes)	High/Low		
Red blood cells	Reticulocytes	High/Low		
White blood cells/differential	Basophils	High		
White blood cells/differential	Monocytes	High/Low
